#### 2.2 Study populations

The following analysis sets will be defined for analysis:

#### Intention to treat (ITT) population

All subjects in the Main Investigational Cohort randomized to the DCVax®-L or placebo arms.

Data will be analyzed for efficacy endpoints according to the subject's randomized allocation.

#### Per Protocol (PP) population

All subjects in the ITT population with the exception of those:

- who did not receive DCVax®-L [or did not receive full treatment] because sufficient vaccine could not be produced;
- who did not receive any DCVax®-L [or did not receive full treatment] for other reasons;
- with other major protocol deviations (as determined at blinded data review), including those who did not receive their randomized treatment at all, for whatever reason.

Subjects will be analyzed for efficacy endpoints according to the first study treatment they received.

All analyses conducted for the primary and secondary endpoints will be repeated for the PP population.

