# **Section 7:** Exposure

The scheduled dosing regimen in the double-blind period comprises 10 administrations. However, some participants in the DCVax®-L treatment arm may not receive 10 immunizations due to insufficient manufacturing material (Protocol Section 3.3) or otherwise. The intended number of cells for each treatment is 2.5 million cells (two injections of 1.25 million cells). The volume of study drug for delivery of that number of cells is participant-specific (Protocol Section 8.1).

Further, all participants in both treatment cohorts whose disease progresses, as defined in Section 15.2 of the protocol, were offered a crossover option at the time of disease progression. All the participants from either arm of the trial who elected to receive DCVax®-L in the crossover, will have re-started the original 10-administration schedule using DCVax®-L, with all parties (patient, investigator, CRO and sponsor) remaining blinded to the patients' original randomized allocation.

For all subjects in both treatment cohorts, the following exposure variables will be calculated for the initial trial period and the crossover period:

- Number of DCVax®-L administrations
- Total number of cells received per administration
- Total number of cells received overall

These will be summarized as continuous variables, by treatment group and overall.

The numbers and percentages of subjects who receive at least 3 administrations, and who receive at least 6 administrations, will also be summarized as categorical variables by treatment group and overall.

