#### 8.1.6 Subgroup analyses for OS and CS

The analyses described for OS and CS will all be repeated for each of the following subgroups, where the data allow.

Table 5: Planned subgroup analyses

Characteristic	Subgroups		
Methylation status (MGMT):	Methylated, unmethylated		
• Extent of resection:	
 
Complete, partial
 
		
	
 
Significant, minimal residual
 
		
Age categories:	• 18-40, 41-50, 51-60, 61-64, ≥65		
• Sex:	
 
Male, female
 
		
• KPS:	

70 – 80, > 80 - 90, > 90 – 100

		

 
Baseline lymphocyte count (/μL):
 
	• ≤ median, > median		
	

≤ 1,000, > 1,000

		
	• ≤ 1,250, > 1,250		

 
RPA classification:
 
	
 
Class III, Class IV
 
		
• Race:	
 
Caucasian, non-Caucasian
 
		

 
Residual tumor size:
 
	
 
Measurement; also quartiles
 
		

 
PD-L1 expression in tumor tissue:
 
	

High, Low

		

 
PD-L1 status of circulating monocytes:
 
	
 
> 80% positive cells, ≤ 80%
 
		
	
 
> 50% positive cells, ≤ 50%
 
		
	
 
>10% positive cells, ≤ 10%
 
		

 
Pre-existing CD8 T-cell density:
 
	• ≤ median, > median		

 
Immunological responders to DCVax®-L:
 
	• Yes, No		

 
Histology - GBM subtype:
 
	
 
Proneural, Neural, Classical,
 
		
	Mesenchymal		
• Immunoscore:	• 0 through 5		
Biomarker status:	
 
EGFR and PTEN genes, IDH1 WT,
 
		
	1p19q intact		

 
Rapid progressors (subjects with PFS ≤ 2m):
 
			
	• Yes, No		

 
Early progressors: (subjects with PFS ≤ 4m):
 
	• Yes, No		

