#### **Treatment Schedule:**

Two intradermal (i.d.) injections of DCVax-L (active) or autologous MNC (placebo) per treatment; each injection consisting of 1.25 million DC in approximately 0.15 mL, in the upper arm. Injection volume is patient specific and the Certificate of Analysis (C of A) should be referenced. Treatments will be given at days 0, 10, 20, and at months 2, 4, 8, 12, 18, 24 and 30. All Crossover patients will receive the active immunization injections on this schedule, study drug supply availability permitting.

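### The per-protocol set is defined by receipt of DCVax-L in both arms: read literally it drops placebo patients who never crossed over, and an undefined bracketed clause could select survivors

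*Combined protocol and SAP*

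**What the plan says.** SAP Section 2.2 starts the PP set from "All subjects in the ITT population with the exception of those" who meet any of three conditions. The first covers patients "who did not receive DCVax®-L [or did not receive full treatment] because sufficient vaccine could not be produced". The second covers those "who did not receive any DCVax®-L [or did not receive full treatment] for other reasons". The third covers other major protocol deviations judged at blinded review, "including those who did not receive their randomized treatment at all, for whatever reason". The first two conditions are not limited to the DCVax-L arm, full treatment is not defined, and there is no exception for death or progression. PP patients are then analysed under whichever study treatment they received first.

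The same section adds: "All analyses conducted for the primary and secondary endpoints will be repeated for the PP population". PP is also named beside ITT for primary Analysis #1 (SAP Section 1.2.1) and in Table 2 (SAP Section 3.1). The opening of SAP Section 6 says that formal claims are made on ITT.

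On exposure, SAP Section 7 states: "The scheduled dosing regimen in the double-blind period comprises 10 administrations". The protocol synopsis gives the timing: "Treatments will be given at days 0, 10, 20, and at months 2, 4, 8, 12, 18, 24 and 30". Placebo patients can receive DCVax-L only through the crossover offered once progression is established (Protocol Section 8.4).

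**The concern.** A PP set should reflect adherence to each arm's own assignment. Here membership depends on receiving DCVax-L after randomization, whichever arm the patient is in. Two consequences follow.

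First, a placebo patient who completes the blinded course as assigned but never crosses over has received no DCVax-L and is excluded. Crossover requires progression, so the placebo group that remains is conditioned on progressing and then living long enough to be treated. The DCVax-L arm faces no such condition.

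Second, if the bracketed words are operative, a DCVax-L patient who dies before completing the course is excluded, while an external control who dies at the same time is kept. That favours DCVax-L even if the product does nothing.

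At stake is the credibility of the PP results as support for ITT, and whether the set can be programmed without a choice of meaning being made after unblinding.

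**Working it through.** The plan gives no PP count or expected PP effect, so there is no stated figure to reproduce. The design event counts do not bear on this point.

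**Inputs.** ITT 331 (SAP Section 1); DCVax-L arm 232 (SAP Section 1.2.1); hence placebo 331 − 232 = 99. External controls: n = 1,366, median OS 16.5 months (SAP Section 8.1.3). Design median OS for DCVax-L: 25.3 months (SAP Section 1.3.2), used as a second case. Doses 5, 6 and 10 fall at months 4, 8 and 30, with a 28-day month (Protocol Section 3.3).

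**Step 1: placebo patients removed.** 90% of 331 is 297.9, leaving about 33.
- SAP Section 1.2.3 (Secondary Endpoint #4) says 90% of all patients received DCVax-L. If all 232 in the DCVax-L arm did, the 33 are all placebo: 33 of 99. If all 33 were in the DCVax-L arm, the count is 0.
- SAP Section 1.1 says about 90% of all patients crossed over. If that holds equally in each arm, 10% of 99 is about 10.

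The range is therefore 0 to 33.

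**Step 2: which analyses this touches.** The primary comparison uses only the patients randomized to DCVax-L (SAP Sections 1.2.1 and 8.1.5), so it does not. Secondary Endpoint #1 already consists of placebo patients who crossed over. The within-trial PP comparisons of confirmed PFS, PFS and OS are affected. For PFS and confirmed PFS, the placebo arm loses its progression-free patients while the DCVax-L arm keeps its own. For OS, both early deaths before crossover and non-progressors are lost, so the direction is unclear.

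**Step 3: time needed to reach a dose.** T = months × 28 / 30.4375.
- Dose 5: 112 days = 3.7 months.
- Dose 6: 224 days = 7.4 months.
- Dose 10: 840 days = 27.6 months.

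**Step 4: share alive at T.** With exponential survival and median M, S(T) = 0.5^(T/M). At M = 16.5:
- Dose 5: 0.857 × 232 ≈ 199.
- Dose 6: 0.734 × 232 ≈ 170.
- Dose 10: 0.314 × 232 ≈ 73, with median OS among those kept of 27.6 + 16.5 = 44.1 months.

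**Step 5: hazard ratio with no drug effect.** 300 simulated trials per case: 232 DCVax-L patients, keeping only those alive at T, against 1,366 unfiltered controls with the same median; censoring at 60 months; Cox model.

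| Meaning of the clause | HR, median 16.5 in both | HR, median 25.3 in both |
|---|---|---|
| Clause dropped (any DCVax-L) | 1.00 | 1.00 |
| 5 doses | 0.86 | 0.89 |
| 6 doses | 0.74 | 0.79 |
| 10 doses | 0.39 | 0.43 |

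**The case against.** The strongest reply is that PP carries no formal weight. Claims rest on ITT (SAP Section 6), the within-trial OS and PFS tests are on ITT (SAP Section 8.3.2), the PP Cox model for those endpoints is listed as exploratory (SAP Section 8.3.4), and the alpha split in SAP Section 8.1.1 gives PP no separate share. This stands. In the simulations, a nominal one-sided 2% test crossed its threshold in every ten-dose run, but that is not a type I error rate of the trial. What remains is that PP is still reported beside ITT for the primary and secondary endpoints, where it will be read as corroboration.

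A second reply is that the first two exclusions were meant only for the DCVax-L arm. The third exclusion and the rule of analysing by first treatment both suggest so. That is plausible, but the text does not say it.

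A reader might infer that the PP set keeps only patients who completed all ten doses, and that an apparent benefit is therefore guaranteed. The documents do not support this. The clause is bracketed and undefined, and other text points away from ten doses: patients receive up to ten, randomization requires only five available, exhausted doses are replaced by placebo (protocol synopsis), and exposure is summarized at three or more and six or more (SAP Section 7). If the clause falls away, the survivor selection in the DCVax-L arm disappears.

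**Conclusion.** The concern holds in two parts of different certainty.

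The placebo exclusion follows from the literal text whether or not the brackets apply. It removes 0 to 33 of 99 patients and distorts the within-trial PP analyses of PFS, confirmed PFS and OS, with no predictable direction for OS. The figure of 33 is the top of the range, not an estimate.

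The survivor selection is conditional on the bracketed clause. With no drug effect, the PP hazard ratio against external controls runs from 1.00 (clause dropped) through about 0.86 and 0.74 (5 and 6 doses) to about 0.4 (10 doses, about 73 of 232 kept) at a 16.5-month median, and is slightly milder at 25.3 months. These figures assume exponential survival, censoring at 60 months, at least one dose in all 232, and the randomized dose schedule as the clock, without counting doses from a restarted crossover course.

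A reader might also infer that the formal primary result is compromised. It is not, because formal claims are made on ITT. The bias is confined to PP results.

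**What to change.** Change the wording of SAP Section 2.2 before unblinding:

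- Delete both bracketed clauses.
- Replace the first two exclusions with one: patients who never received their own randomized study treatment.
- Keep the other major protocol deviations, as judged at blinded data review.
- State that death, progression or exhausted supply before later doses is not a reason for exclusion.
- Reconcile SAP Sections 1.1 and 1.2.3 on whether 90% crossed over or 90% received DCVax-L.

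If a dose-based set is wanted, state the threshold and use a landmark in both groups: include only patients alive at that time and start the clock there. The SAP already applies this symmetry to conditional survival (Section 3.1.2). The downside is that MAIC matching would not be available with published data alone, as SAP Section 8.1.5 acknowledges for conditional survival.

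The cost is SAP text only. PP results will sit closer to ITT.

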#### Safety population

All subjects in all three cohorts who received at least one immunization with DCVax®-L or placebo. Subjects will be analyzed for safety endpoints according to the treatment they actually received. Subjects will be analyzed in aggregate as well as separately by cohort. Subjects will be analyzed for efficacy endpoints according to their randomized allocation.

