#### 1.6.1 Informational cohort

Subjects not eligible for randomization were offered an opportunity to participate in a separate compassionate use treatment cohort since at time of screening for enrolment and randomization,

the personalized DCVax®-L product had already been manufactured. These subjects are referred to as the "Informational Cohort" or "Information Arm" and are not part of the main study.

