#### Note:

- 1. The conditional survival endpoint is calculated in patients reaching the chosen threshold.
- 2. Subgroup analyses will also be conducted.
- 3. The efficacy analysis for the Informational cohort will not be comparative, as there is only one arm, and will only include descriptive statistics.

Safety data will be reported for the Safety population.

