## **Section 9:** Safety

#### 9.1 Adverse events

An overall summary will present the number and percentage of subjects by treatment group with:

- Any TEAE
- Any serious TEAE
- Any TEAE considered as related to study drug, evaluated by the investigator as Definitely Related, Possibly Related or Probably Related or not reported
- Any TEAE considered as related to leukapheresis, evaluated by the investigator as Definitely related, Possibly Related or Probably Related or not reported
- Maximum CTCAE of grades 1 to 5; i.e. a subject with TEAEs at different CTCAE grades will be summarized at the most severe grade
- Any TEAE leading to study drug discontinuation
- Any TEAE leading to death

The summary will also include the total number of TEAEs reported in each treatment group.

The number and percentage of subjects with TEAEs will be presented by SOC, PT and treatment group. Subjects with multiple TEAEs within a SOC or SOC/PT combination will be counted only once for that SOC or SOC/PT combination. Similar summaries will be presented for related TEAEs, serious TEAEs, related serious TEAEs, and TEAEs leading to discontinuation of study drug. TEAEs with CTC Grade 3 or above, and related TEAEs with CTC Grade 3 or above, will be summarized.

Summaries of TEAEs by maximum CTCAE grade will also be presented.

All TEAEs will be listed by subject and start date.

Injection site TEAEs will be listed separately.

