#### Study Design:

The study is designed as a randomized, placebo-controlled, double blinded, multi-center, multi-national Phase III clinical trial.

To achieve its primary goals, the trial will randomize approximately 348 patients with newly diagnosed GBM with no evidence of progression at baseline, of which approximately 232 patients will be randomized into the treatment cohort and will receive DCVax-L as adjuvant therapy to standard treatment and approximately 116 patients will be randomized into the placebo cohort and will receive standard treatment supplemented with autologous mononuclear cells (MNC; placebo).

Patients must have a minimum of 5 doses of DCVax-L available to be eligible for randomization. Randomized patients will receive up to 10 immunizations with DCVax-L or placebo over a period of up to 3 years. Some patients in the DCVax-L cohort may not receive 10 immunizations due to insufficient material; in these cases immunizations will be replaced with placebo while maintaining the blind. Patients in either cohort who progress during the study will be offered a crossover (openlabel) option with no unblinding to receive a series of up to 10 immunizations with DCVax-L (depending on DCVax-L availability).

Safety of DCVax-L will be assessed by comparing the frequency and intensity of adverse events, physical and neurological examination, and clinical laboratory testing results during the study period, between DCVax-L treated patients and controls.

Protocol: 020221, v7.0 23SEP2020 Page 2 of 55

Northwest Biotherapeutics, Inc. DCVax®-L, IND #10206

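### The aggregate safety tables add the single-arm Informational cohort to the DCVax-L column only, and the SAP does not say whether they or the by-cohort tables lead

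*Combined protocol and SAP*

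**What the plan says.** SAP Section 2.2 defines the Safety population as "All subjects in all three cohorts who received at least one immunization with DCVax®-L or placebo". On grouping it says "Subjects will be analyzed for safety endpoints according to the treatment they actually received", and on pooling "Subjects will be analyzed in aggregate as well as separately by cohort".

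Section 2.3 lists the ITT, PP, pseudo-progression and Informational sets separately for demographics and for efficacy. For safety it says only "Safety data will be reported for the Safety population". Section 9.1 begins "An overall summary will present the number and percentage of subjects by treatment group with" and goes on to any TEAE, serious TEAEs, maximum grade and TEAEs leading to death. Section 9 does not mention cohort, and neither section names a lead table.

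On who the Informational patients are, Section 1.6.1 says "Subjects not eligible for randomization were offered an opportunity to participate in a separate compassionate use treatment cohort". Note 3 in Section 2.3 makes their efficacy analysis non-comparative "as there is only one arm". The pseudo-progression cohort was randomised 2:1 (Section 1.6.2).

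The v7.0 protocol synopsis states the purpose of the safety data: "Safety of DCVax-L will be assessed by comparing the frequency and intensity of adverse events", with controls as the comparator. Protocol v7.0 Section 15.6 likewise compares overall AE incidence between the treatment and placebo cohorts.

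**The concern.** Read together, Sections 2.2 and 9.1 produce an aggregate table with a DCVax-L column and a placebo column. Informational patients can appear only in the first. They were not randomised and failed the eligibility rules that the main cohort met, so the two columns differ in case mix as well as in treatment.

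This matters because disease feeds the AE counts. Protocol v7.0 Section 13.2 asks for new or worsening GBM symptoms to be recorded as AEs, and Section 13.3 expects that symptoms of progression may be SAEs. If Informational patients carry heavier disease, all-cause rows in the aggregate DCVax-L column rise for reasons unrelated to the product. Since no lead table is named, those figures could be quoted as the safety profile of DCVax-L against placebo.

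**Working it through.** The plan states no figure for this point, so there is nothing to reproduce. The check traces the text and then illustrates the size.

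**Who is added.** The v4.0 synopsis, from the protocol version that included the Informational arm, describes patients with progressive GBM at the end of chemoradiation and patients found ineligible for other reasons after leukapheresis. V4.0 Section 6.2 also sends patients with equivocal tumour status to that arm. Protocol v7.0 Section 7.2 excludes anyone with evidence of progression at baseline from the randomised study. The cohorts therefore differ by design, but the documents give neither the case mix nor the size of the Informational cohort.

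**Inputs from the documents.** The ITT population is 331 (SAP Section 1), of whom 232 were randomised to DCVax-L (SAP Section 1.2.1). That leaves 331 − 232 = 99 on placebo. These are randomised counts; the number treated is not given.

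**Assumed inputs.** Informational cohort size n; event rate p in both main-cohort arms (no drug effect); event rate q in the Informational cohort.

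**Formula**, leaving out the pseudo-progression cohort:

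- Aggregate DCVax-L rate = (232p + nq) / (232 + n)
- Placebo rate = p
- Spurious difference = n(q − p) / (232 + n)

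The sign follows the sign of q − p. The formula gives a size only once q is assumed.

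**First illustration.** Take p = 40%, n from 20 to 60 and q from 50% to 80%.

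- Low end: (92.8 + 10) / 252 = 40.8%, a difference of 0.8 points
- High end: (92.8 + 48) / 292 = 48.2%, a difference of 8.2 points

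**Wider assumptions.** Spurious difference in percentage points:

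| n | p 30%, q 40% | p 30%, q 70% | p 50%, q 80% |
|---|---|---|---|
| 10 | +0.4 | +1.7 | +1.2 |
| 25 | +1.0 | +3.9 | +2.9 |
| 50 | +1.8 | +7.1 | +5.3 |
| 100 | +3.0 | +12.0 | +9.0 |

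**Main-cohort or cohort-stratified comparison.** A stratum with no placebo patients has Mantel-Haenszel weight 232-type numerator n × 0 / n = 0. The Informational cohort drops out, and under no drug effect the expected difference is 0.

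**Pseudo-progression cohort.** Assume 30 patients (20 DCVax-L, 10 placebo) and p = 30%.

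- Event rate 50%: (69.6 + 10)/252 − (29.7 + 5)/109 = 31.6% − 31.8%, or −0.2 points
- Event rate 70%: (69.6 + 14)/252 − (29.7 + 7)/109 = 33.2% − 33.7%, or −0.5 points

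This cohort brings its own controls, so under these assumptions it shifts the difference very little.

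**Crossover.** The formula treats all 99 placebo patients as placebo throughout. The SAP Executive summary puts crossover at about 90% of all patients, and Section 1.1 says this includes most of the control arm. Section 2.2 groups safety by treatment received without saying where a placebo patient's events after crossover are counted. Section 7 already separates the initial and crossover periods for exposure; Section 9 does not do so for events.

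**The case against.** The strongest reply is that the sentence creating the aggregate also plans tables by cohort. Those give the main cohort by arm, the pseudo-progression cohort by arm and the Informational cohort alone, which meets the comparison in protocol Section 15.6. This stands. A reader might infer that the plan offers no safety comparison free of Informational patients; it does.

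Section 9 of the SAP is also descriptive, with counts, percentages, listings and shift tables and no between-group test. A reader might infer a formal pooled comparison, but none is specified. The two-column aggregate follows from reading Sections 2.2 and 9.1 together. Note 3 in Section 2.3 concerns the Informational cohort's own efficacy analysis, so it is an analogy for safety rather than a contradiction.

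The direction of bias is open too. Some Informational patients were ineligible for reasons other than progression. Section 9.1 reports the percentage of subjects with events, not rates per time at risk. AE collection ends 30 days after the patient leaves the trial or after the last treatment, whichever is later (protocol Section 13.2). Patients with shorter survival or fewer doses may therefore show fewer events. Rows for related events depend on investigator attribution, which should limit the effect there.

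Finally, pooling all exposed patients helps to detect uncommon events, and an inflated DCVax-L column would overstate harm rather than hide it. Both points are fair. They support an aggregate of exposed patients, but not a placebo column beside it.

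**Conclusion.** The point holds as a minor one. The aggregate DCVax-L versus placebo difference is not a randomised comparison, whichever way it leans, and the SAP does not say which set of tables leads. All-cause TEAEs, serious TEAEs, grade 3 or higher events and deaths are probably affected most.

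A reader might go further and conclude that the Informational patients' disease burden will be counted as DCVax-L harm. The documents make that likely for the aggregate all-cause rows but do not establish it, because they give no cohort size, case mix or event rates. The 0.8 to 8.2 points, and the wider 0.4 to 12.0, are illustrations: every scenario assumes a higher event rate in the Informational cohort, and that assumption produces the positive sign.

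Restricting the tables to the main cohort removes the cohort confounding. It does not by itself give a clean randomised contrast, because the handling of crossover patients is unspecified.

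**What to change.** In SAP Sections 2.2 and 9:

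- Name the randomised main-cohort table as the lead DCVax-L versus placebo safety comparison.
- In that table, separate events before crossover from those after it, so that post-progression DCVax-L exposure stays out of the randomised contrast. The period split in Section 7 can be reused.
- Show the pseudo-progression cohort by its own randomised arms.
- Report the Informational cohort single-arm. V4.0 Section 13.9 already planned to tabulate its AEs apart from the treatment versus placebo comparison.
- Present any aggregate as one column of all DCVax-L exposed patients, with no placebo contrast.

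The cost is SAP wording and table shells. No data are lost, and the aggregate remains available for uncommon events.
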